Objectives	
Primary:
 
Determine if intra-pyloric botulinum toxin injection (Botox[®]) during a minimally invasive esophagectomy decreases postoperative occurrence of delayed gastric emptying. 
Secondary:
 
Determine if intra-pyloric botulinum toxin injection during a minimally invasive esophagectomy:
Reduces the number of repeat procedures for delayed gastric emptying within 90 days,Decreases time to oral intake meeting 100% of nutritional requirements,Reduces the incidence of pulmonary complications directly related to delayed gastric emptying,Reduces hospital length of stay related to delayed gastric emptying and,Increases patient quality of life.
Study Design	Double-arm, randomized, Phase II study
Target Accrual and Study Duration	A maximum of 50 evaluable patients at RPCI will be enrolled. Accrual is expected to take up to 6 years. Study participants will be followed for data collection for 90 days (routine post-esophagectomy follow-up care and surveillance, per standard of care). Data will be collected for 90 days on each patient.
Study Procedures	
Medical History, Pre-Existing Conditions (including smoking status and diabetes): Baseline
 
Disease Evaluation (Multidisciplinary evaluation and neoadjuvant therapy for esophageal carcinoma): Baseline
 
Hematology, Chemistry: Baseline, Postoperative course
 
Performance Status: Baseline
 
Physical Examination (including neurological examination, vital signs, and body weight): Baseline, Inpatient and Outpatient Postoperative Course
 
Electrocardiogram, Chest x-ray, and/or Pulmonary Function tests: At baseline, if clinically indicated.

	
Pregnancy test (urine): Baseline
 
Gastrograffin swallow or CT esophagram: Surgery to Discharge
 
Nuclear Medicine Emptying Study: Post Op Visit 2 (+/- 14 days)
 
Medical and Clinical Evaluation of Delayed Gastric Emptying: Inpatient and Outpatient Postoperative Course
 
Clinical Events of Interest and Adverse Events: During surgical procedure, Inpatient and Outpatient Postoperative Course
 
Nutrition Evaluation: At baseline, if indicated and, Inpatient and Outpatient Postoperative Course
 
EORTC QLQ OES18 Questionnaire: Outpatient postoperative course

Statistical Analysis	
Sample Size Determination: The sample size justification is based on the primary analysis. We consider a study design with a total sample of n=50 patients (randomly assigned in a 1:1 fashion to the Botox and non-Botox treatment arms) and an interim analysis at n_i=30. The performance of this study design and decision rules (described in the primary analysis) was assessed via simulation study.
 
Randomization: Patients will be randomized in a 1:1 fashion to the Botox and non-Botox treatment arms using a permuted block design. The randomization list will be developed by the Department of Biostatistics and Bioinformatics.
 
Primary and Secondary Analyses:
 
Primary Analysis: A recent study demonstrated that patients that received Botox had a delayed gastric emptying rate of approximately 30% as compared to a complication rate in historical controls of 70% in patients that did not receive botulinum toxin (Botox) (1). A retrospective review of patients undergoing minimally invasive esophagectomy at Roswell Park Cancer Institute indicates that the rate of postoperative delayed gastric emptying is even lower. Therefore, the primary objective is to determine if intra-pyloric botulinum toxin injection during a minimally invasive esophagectomy decreases postoperative occurrence of delayed gastric emptying. The primary outcome is delayed gastric emptying (assessed radiographically by nuclear medicine emptying study) which is treated as a dichotomous variable.
 
Patients will be stratified by receipt of neoadjuvant chemoradiotherapy, smoking status, and diabetes; and randomized in a 1:1 to the botulinum and non-botulinum treatment arms. The primary objective will be assessed using the intent-to-treat principle and a one-sided Cochran-Mantel-Haenszel (CMH) s test about the following hypotheses:
 $H_0: \theta \geq 1,$ $H_A: \theta < 1$ 
where θ is the common odds ratio (COR) for the odds of delayed gastric emptying rates for the botulinum versus non-botulinum treatment arms. A one-sided test is performed as the rate of delayed gastric emptying is expected to decrease in the botulinum arm over the non-botulinum arm; that is we expect $\theta < 1$.

The analysis will proceed in two stages using an O'Brien-Fleming alpha spending function. An interim analysis will be conducted after $n_1=30$ patients have completed treatment and the final analysis will be conducted after $n=50$ patients have completed treatment. The following decision rules will be utilized at each analysis:

Analysis	Decision Rule
Interim	
• If $p\text{-value} \leq 0.011396$, then reject H_0 and stop due to superiority.• If $\hat{\theta} > 1$, then stop due to inferiority.• Otherwise enroll $n_2=20$ patients.
Final	
• Reject H_0 if $p\text{-value} \leq 0.046533$

Secondary Analysis: The secondary outcomes include additional postop procedures, clinically assessed delayed gastric emptying (days to resumption of oral feeding, EORTC QLQ-30 QoL scores, and clinical symptoms of regurgitation, vomiting, and aspiration), delayed gastric emptying assessed by the gastrografin swallow exam or CT esophagram, pulmonary complications (aspiration, respiratory failure requiring reintubation, pneumonia within 3 months of surgery), and hospital length of stay. All variables will be reported by treatment arm using the appropriate descriptive statistics and graphical summaries.

**INVESTIGATOR STUDY ELIGIBILITY VERIFICATION FORM
INCLUSION CRITERIA**

Participant Name: _____

Medical Record No.: _____

Title: Double-arm, Randomized Study of Botulinum Toxin Injection as a Pyloric Drainage Procedure for Minimally Invasive Esophagectomy (Phase II)

INCLUSION CRITERIA				
Yes	No	N/A	All answers must be "Yes" or "N/A" for participant enrollment.	Date
			1. Esophageal carcinoma, undergoing minimally invasive esophagectomy with intrathoracic anastomosis.	
			2. Age \geq 18 years of age.	
			3. Have an ECOG Performance Status \leq 2. Refer to Appendix A .	
			4. Participant or legal representative must understand the investigational nature of this study and sign an Independent Ethics Committee/Institutional Review Board approved written informed consent form prior to receiving any study related procedure.	

Investigator Signature: _____ **Date:** _____

Printed Name of Investigator: _____

**INVESTIGATOR STUDY ELIGIBILITY VERIFICATION FORM
EXCLUSION CRITERIA**

Participant Name: _____

Medical Record No.: _____

Title: Double-arm, Randomized Study of Botulinum Toxin Injection as a Pyloric Drainage Procedure for Minimally Invasive Esophagectomy (Phase II)

EXCLUSION CRITERIA				
Yes	No	N/A	All answers must be "No" or "N/A" for participant enrollment.	Date
			1. Patients who have a history of gastrointestinal dysmotility or functional gastroparesis, including diabetic gastroparesis, central and peripheral nervous system disorders, renal failure, medication side effects, including chronic dependence of promotility agents, anticholinergic antispasmodic agents, or chronic narcotic use over 2 years due to non-cancer causes. Refer to Appendix B for a list of pharmacologic agents.	
			2. Patients who have a history of previous gastric or duodenal surgery.	
			3. Patients who have a history of duodenal ulcer or duodenal fibrosis.	
			4. Uncontrolled intercurrent illness including, but not limited to, ongoing or active infection, symptomatic congestive heart failure, unstable angina pectoris, cardiac arrhythmia, or psychiatric illness/social situations that would limit compliance with study requirements.	
			5. Allergy to botulinum toxin, and or egg	
			6. Pregnant or nursing female participants.	
			7. Unwilling or unable to follow protocol requirements.	
			8. Any condition which in the Investigator's opinion deems the participant an unsuitable candidate for study participation.	

Participant meets all entry criteria:

Yes **No**

If "NO", do not enroll participant in study.

Investigator Signature: _____ **Date:** _____

Printed Name of Investigator: _____

TABLE OF CONTENTS

1	Background	11
1.1	Minimally Invasive Esophagectomy for Esophageal Carcinoma.....	11
1.2	Risks and/or Benefits.....	12
2	Rationale.....	13
3	Objectives.....	13
3.1	Primary Objective.....	13

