6.2 Baseline Evaluations

Preoperative workup and multimodality therapy for esophageal cancer as standard of care at RPCI, based upon the NCCN guidelines for esophageal cancer. Standard presurgical assessment with full medical history and physical examination, laboratory tests, cross-sectional imaging and cardiopulmonary assessment as determined by the operating surgeon or the Preoperative Anesthesia Clinic based upon RPCI established guidelines.

The following will be performed prior to the participant's scheduled minimally invasive esophagectomy and will be confirmed before surgery:

- Informed consent for study. Must be completed prior to receiving any study-related procedures.
- Medical history with preexisting conditions, including all neoadjuvant therapy related to esophageal carcinoma, smoking status and, diabetes.

- Physical examination, including vital signs (i.e., temperature, heart rate, respiratory rate, blood pressure), body weight and height; with emphasis on the neck, thoracic, and abdominal cavities.
- Multidisciplinary evaluation and neoadjuvant therapy if indicated for esophageal carcinoma. Multidisciplinary evaluation will be documented in the outpatient preoperative office visit note.
- Pregnancy test (urine) in females of childbearing potential. The standard operating procedure for all females of childbearing potential in the Ambulatory Surgical Center (ASC) pre-op holding area is to obtain a urine HCG. This study protocol does not deviate from the standard operating procedure of the ASC/pre-op holding area at RPCI. If the pregnancy test is positive, the patient is excluded from the study.
- Nutritional status assessment by a dietitian, as clinically indicated.

The following will be performed if indicated by the anesthesia pre-op assessment (standard operating procedure for the pre-op clinic at RPCI). These tests are not strictly required to support eligibility for this study, but if indicated and performed, may exclude the patient from receiving a general anesthetic and thereby excluding the patient from this study.

- Hematology: CBC with automated differentials (WBC, RBC, HGB, HCT, platelet, MCV, MCH, MCHC, % neutrophils, absolute neutrophils, % monocytes, absolute monocytes, % eosinophils, absolute eosinophils, % basophils, absolute basophils, % lymphocyte, absolute lymphocyte, platelet confirmation (as clinically indicated), and differential confirmation (as clinically indicated).

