6.4 Inpatient Postoperative Follow-Up Evaluations

The following evaluations will be performed during the **inpatient postoperative course (surgery to discharge), unless otherwise clinically indicated.**:

Patients will follow Roswell Park standard of care postoperative pathway for minimally invasive esophagectomy (refer to Section 4.1), unless otherwise clinically indicated. This includes:

- Initial postoperative care in the intensive care unit or intermediate care unit, based on clinical status, with nursing care and vital signs per hospital unit standard:
- At the minimum daily physical examination (including vital signs).
- Laboratory analysis, including hematology (CBC with automated differentials) and chemistry (CMP), at least on a daily basis until Postoperative Day 6.
- Standard inpatient postoperative evaluations after minimally invasive esophagectomy include daily chest x-ray for at least four days postoperatively, and occasionally a CT scan of the chest if clinically indicated.
- Gastrograffin swallow study/CT esophagram is obtained to evaluate for any signs of anastomotic leak.
- Clinical evaluation of symptoms will be evaluated by the participant's care team, including inpatient nurses, mid-level providers, surgical fellows, operating surgeon, speech therapist, occupational or physical therapists, dieticians, and documented in the RPCI electronic medical record (EMR).
- Speech therapy evaluation for any dysphagia or signs of aspiration.
- Nutritional assessments will be performed by a dietitian familiar with the study. The initial evaluation will be performed in the outpatient setting if there are signs of malnutrition or inability to tolerate oral intake at the preoperative visit. Otherwise the standard is to perform the initial nutritional assessment in the immediate postoperative period. Patients will be monitored by the dietitian Monday-Friday while an inpatient, and then at each subsequent follow-up office visit, and assessment documented in the RPCI EMR.
- Nutritional goals are as follows: By hospital discharge, patients are expected to meet 50% of their total nutritional requirements orally and 50% by supplemental j-tube feeds. On

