6.6 Outpatient Postoperative Follow-Up Visits

Study participants will be followed for data collection for 90 days (routine post-esophagectomy follow-up and surveillance, per standard of care). The following evaluations will be performed during the outpatient postoperative course, unless otherwise clinically indicated:

- In the postoperative period, patients return to office for outpatient follow-up approximately one to three weeks after discharge (“Postoperative Visit #1”). This visit is standard of care and can be scheduled per PI discretion. Physical exam and vital signs will be conducted at this visit. The dietician will assess oral intake, and supplemental tube feeds adjusted accordingly. Day until patient tolerates 75% and 100% of nutritional needs orally will be recorded as per nutritionist assessment.
- As a participant in this study, patients in both randomization groups will undergo a nuclear medicine emptying study. The nuclear medicine emptying study may occur within the window of Postoperative Visit #2 (\pm 14 days) to assess dynamic conduit function. This test can be extended beyond post-operative Visit #2 at PI’s discretion. Patients will be monitored for any symptoms of delayed gastric emptying during this time by questionnaire (See **Appendix C**), to determine if nuclear medicine study findings correlate with concurrent clinical symptoms.
 - Prior to the nuclear medicine emptying study, the patient must be fasting for at least 6 hours, including oral intake and any supplemental j-tube feeds. If the patient is a diabetic, the glucose level should be measured and less than 275 mg/dL within 2 hours of the study. Opiates must be held for 48 hours prior to the study. Patients should not be on any of the medications listed in **Appendix B** within the 48 hours prior to the study. Patients will remain in the nuclear medicine suite during this time, and will be required to sit upright, and may walk around the room. During the study, for the time between the images, the patients may be sitting, standing, or walking, but should remain in close proximity to the nuclear medicine facility.
- Post-surgical symptom evaluation based on clinical factors during the outpatient follow-up visits, and additionally by phone conversation between outpatient follow-up appointments if clinically indicated.

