Medical evaluation (signs of pneumonia, aspiration)			X	X	X	
Nutrition evaluation ¹³	X (As indicated)		X ¹⁴	X	X	X (As indicated)
EORTC QLQ OES18 Questionnaire ¹⁰ See Appendix D					X	
Pregnancy Test ⁷ (Urine)	X					
Electrocardiogram, Chest x-ray, and/or Pulmonary Function tests	X (As indicated)					
Speech therapy evaluation			X (As indicated)			
Concomitant Medications	X ⁸	X	X	X	X	X
Clinical Events of Interest and AEs		X ⁹	X	X	X	X

Evaluation	Baseline ¹	Day of Surgery	Inpatient Postoperative Course ² (Surgery to Discharge)	Postoperative Visit #1 ³ ± 14 days	Postoperative Visit#2 ³ ± 14 days	End of Study phone call Day#90 (± 14 days)
Fasting glucose (for patients with diabetes)					X (As indicated)	

1 Baseline evaluations will be performed prior to the participant's scheduled minimally invasive esophagectomy and will be confirmed before surgery (Preoperative workup and multimodality therapy for esophageal cancer as standard of care at Roswell Park and based upon the NCCN guidelines for esophageal cancer. Refer to Section 6.2).

2 Patients will follow the standard of care postoperative pathway for minimally invasive esophagectomy.

3 Initial Standard of Care postoperative follow-up visit (Postoperative Visit #1) after hospital discharge, and then again at Postoperative Visit #2 if the postoperative course is uncomplicated. If complications arise, patients may be seen more often in follow-up. Patients will be followed for data collection for 90 days following surgery.

4 Vital signs (temperature, heart rate, respiratory rate, blood pressure), body weight and, height. Height collected at baseline only.

5 If indicated by the anesthesia pre-op assessment- Hematology: CBC with automated differentials (WBC, RBC, HGB, HCT, platelet, MCV, MCH, MCHC, % neutrophils, absolute neutrophils, % monocytes, absolute monocytes, % eosinophils, absolute eosinophils, % basophils, absolute basophils, % lymphocyte, absolute lymphocyte, platelet confirmation (as clinically indicated), and differential confirmation (as clinically indicated).

6 If indicated by the anesthesia pre-op assessment - Chemistry: CMP (chloride, CO₂, potassium, sodium, BUN, glucose, calcium, creatinine, total protein, albumin, total bilirubin, alkaline phosphatase, AST, ALT, A/G ratio, BUN/creatinine ratio, osmol (Calc), anion gap), as clinically indicated.

7 To be performed < 1 week prior to scheduled surgery,

8 Medications ongoing, or discontinued, within 1 week prior surgery.

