7 SAFETY EVALUATION

7.1 Clinical Events of Interest and Adverse Events

Clinical events of interest (captured in REDCap) include, but are not limited to: patient continues to require supplemental jejunal feeds, persistent clinical symptoms of delayed gastric emptying (delayed gastric emptying assessed by the gastrografin swallow exam/CT esophagram), subsequent pneumonia, aspiration events, respiratory failure requiring reintubation, nausea, vomiting, ability to eat solid food or drink liquids or having any trouble eating, early satiety, difficulty swallowing saliva, bile or green staining on pillow while sleeping, experiencing acid indigestion or heartburn, pain with eating, additional postop procedures, EORTC QLQ-30 QoL scores, and hospital length of stay.

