7.1.2 Drug Information- Botulinum toxin

OnabotulinumtoxinA (botulinum toxin type A, Botox[©]) inhibits the release of acetylcholine from nerve endings at neuromuscular junctions in the local muscle (10). Without the release of acetylcholine, neurotransmission between peripheral nerve endings and muscle fibers cannot occur, and the muscle becomes weak or paralyzed (10). The inhibitory effect of botulinum toxin is temporary, and muscle function recovers at 3 months after administration. The effect is not immediate, and rather occurs within 1-3 days.

With intramuscular injection at a dose of 100 units, botulinum toxin is not expected to be in contact with the peripheral blood (10). In rare instances, botulinum toxin may spread from the area of injection and produce symptoms consistent with botulinum toxin effects (13). These unanticipated symptoms may include asthenia, diplopia, ptosis, dysphagia, dysphonia, urinary incontinence, and breathing difficulties. These symptoms have been reported hours to weeks after injection.

Incidence of side-effects depends on injection site location. For example, patients treated with botulinum toxin injection into the sternocleidomastoid muscle for cervical dystonia are more likely to have the side-effects of swallowing difficulties, due to local diffusion. Swallowing and breathing difficulties may be life-threatening, and there have been reports of death (11). Patients with history of underlying conditions predisposing to muscle weakness have an increased risk of these side effects occurring (11). However, due to the nature of this study, patients with underlying muscle weakness are excluded from this study.

The maximum recommended dose of OnabotulinumtoxinA, regardless of the indication, is 400 units over three months (10). Cervical dystonia is treated with doses ranging from 198-300 units, divided among the affected muscle, with maximum dose 50 units per site. Our proposed dosage, 100 units in divided doses into the pyloric muscle, is within the range used among other high-volume esophagectomy centers (2, 3, 8, 9).

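### The synopsis includes a neurological examination that Section 6 and Table 2 do not name, and five of the seven listed toxin-spread symptoms are not systematically or comparably solicited in the two arms

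*Combined protocol and SAP*

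**What the plan says.** The Study Procedures entry of the synopsis reads "Physical Examination (including neurological examination, vital signs, and body weight): Baseline, Inpatient and Outpatient Postoperative Course". A neurological examination is thus part of the physical examination before surgery, in hospital and after discharge.

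The procedural sections describe that examination differently. Section 6.2 asks at baseline for vital signs, "body weight and height; with emphasis on the neck, thoracic, and abdominal cavities". Section 6.4 asks for at least a daily physical examination with vital signs. Section 6.6 says of Postoperative Visit #1: "Physical exam and vital signs will be conducted at this visit". The Table 2 row schedules a physical examination with vital signs at baseline, surgery, inpatient, Visit #1 and Visit #2. Footnote 4 to that row lists "Vital signs (temperature, heart rate, respiratory rate, blood pressure), body weight and, height".

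On the drug risk, Section 7.1.2 says the toxin may in rare instances spread from the injection site: "These unanticipated symptoms may include asthenia, diplopia, ptosis, dysphagia, dysphonia, urinary incontinence, and breathing difficulties". Reported onset is hours to weeks after injection, and the section calls swallowing and breathing difficulties potentially life-threatening.

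The clinical events of interest in Section 7.1 are mostly symptoms of delayed emptying, for example "difficulty swallowing saliva, bile or green staining on pillow while sleeping, experiencing acid indigestion or heartburn, pain with eating". The day-90 call in Section 6.7 follows a similar list and adds a general assessment of adverse events.

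**The concern.** Staff following Section 6 and Table 2 would find nothing telling them that a neurological examination is expected. Without a recorded neurological baseline, a later finding of weakness, ptosis or voice change is hard to date or attribute.

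Some of the listed symptoms also resemble ordinary problems after esophagectomy. The postoperative pathway in Section 4.1 already treats hoarseness and aspiration as things to watch for. Separating a toxin effect from an effect of the operation therefore depends on asking the same questions in the same way in both arms.

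This bears on how the result will be read. Section 1.2 gives avoidance of the medication's side effects as one reason the injection might be dropped. If those side effects are collected unevenly, the trial can say little about that part of its own argument.

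**Working it through.** No figure in the plan has to be reproduced here. The check is a comparison of texts, followed by one bound.

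**Step 1: where the neurological examination is named.** It is named in the synopsis. It is named in 0 of 5 procedural places: Section 6.2, Section 6.4, Section 6.6, the Table 2 row, and footnote 4.

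**Step 2: the seven Section 7.1.2 symptoms against what patients are asked.**

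| Symptom | Events of interest (7.1) | Day-90 call (6.7) | OES18 (Appendix D), once at Visit #2 |
|---|---|---|---|
| Dysphagia | swallowing saliva, trouble eating | same | items 34 and 35, among others |
| Breathing difficulties | only respiratory failure with reintubation | respiratory failure | none |
| Dysphonia | none | none | item 43, trouble talking |
| Asthenia | none | none | none |
| Diplopia | none | none | none |
| Ptosis | none | none | none |
| Urinary incontinence | none | none | none |

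Two of 7 have at least a partial counterpart in the event list and the call, and 7 − 2 = 5 have none. Counting OES18, 5 − 1 = 4 have no specific item. The questionnaire in Appendix C asks about eating and gut symptoms and does not change the count. Sections 4.1 and 9.4 also mention the core EORTC questionnaire, but Appendix D reproduces only items 31 to 48, so the core items could not be counted.

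**Step 3: timing of the OES18 item.** It is usually given in postoperative week six to eight and asks about the past week. Six weeks is day 42, so recall begins at about day 42 − 7 = 35. For a patient still in hospital it is given between days 35 and 42, so recall begins no earlier than day 35 − 7 = 28. Voice change that began and resolved before then would be missed by this item.

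**Step 4: what general adverse event collection adds.** The definition in Section 7.1.1 covers any unfavourable sign or symptom. The routine reporting table in Section 7.1.4, however, takes grade 1 and 2 events only when attribution is possible, probable or definite. Section 7.1.3 has the investigator assign attribution, and it defines those three categories by timing relative to drug administration. Section 4.1 blinds the patient and the radiologist but not the surgeon. The same mild diplopia could therefore be reported in an injected patient and, judged unrelated, go unreported in a control. Section 9.4.1 then summarises adverse events by grade and does not mention arm.

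**Step 5: what zero events could show.** Fifty patients at 1:1 gives 50/2 = 25 exposed. With zero events and complete ascertainment, the upper one-sided 95% bound is 1 − 0.05^(1/25) = 0.113, or 11.3%. If the trial stopped at the interim analysis with 30/2 = 15 exposed, it would be 1 − 0.05^(1/15) = 0.181, or 18.1%.

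**The case against.** The strongest reply is that the protocol is not blind to this toxicity. The two symptoms it calls life-threatening both have counterparts in the event list. Section 6.4 sends any dysphagia or sign of aspiration to speech therapy, and OES18 asks both arms about swallowing saliva, choking and talking. The event list is explicitly open-ended, the day-90 call also assesses adverse events, and inpatients are examined at least daily, when early-onset symptoms would appear. All of this stands. A reader might infer that toxin spread would not be looked for at all; the documents do not support that.

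It is also fair to say that the procedural text is silent on the neurological examination and does not exclude it. An examination "with emphasis on the neck, thoracic, and abdominal cavities" can still include other systems, and footnote 4 does not define the whole examination. This too stands. The point is that two descriptions of one procedure differ, not that one forbids the other.

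A third reply is that estimating toxin-spread rates is not an objective, that the injection is part of this centre's standard operation, and that 25 patients say little about a rare event. That is correct and limits the importance of the point. It does not answer the uneven capture, which comes from the attribution filter and the partial blinding rather than from the sample size.

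Two further inferences should be resisted. One is to widen the 11.3% bound for missed cases: the documents give no detection rate. The other is to read a number of further injections from the 300-unit limit in Section 6.5: that section states no dose per retreatment.

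**Conclusion.** The point holds in a limited form. The synopsis includes a neurological examination that none of the five procedural places names. Five of the seven Section 7.1.2 symptoms are absent from both the event list and the day-90 call, and dysphonia has only a single late question in OES18. These symptoms are recordable, but they are not systematically or comparably solicited, and mild cases face a reporting rule that depends on an attribution not stated to be blinded.

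The consequence is for safety ascertainment and the comparison of side effects between arms. Sample size, power and the primary analysis are untouched.

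The 11.3% bound assumes 25 exposed patients and complete ascertainment. Interim stopping, replacement of patients under Section 4.2, and retreatment with botulinum in either arm under Section 6.5 could all change the number exposed. Even with the fix, an absence of events would be weak evidence of safety.

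**What to change.** 1. Reconcile the synopsis with Sections 6.2, 6.4 and 6.6 and with Table 2 and footnote 4, so that the schedule states whether the neurological examination is done and at which contacts. Which version applies is for the sponsor to state.
2. Add the seven Section 7.1.2 symptoms as fixed yes/no items to the clinical events of interest. Collect them at the existing inpatient and outpatient contacts, where onset within hours to weeks would fall, and at the day-90 call.
3. Ask both arms in the same words, and record the answers whatever the attribution.
4. State in Section 9.4.1 that these items and the adverse events are tabulated by arm as well as by grade.

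The cost is wording in Section 6, Table 2, the call script and Section 9.4.1, plus seven eCRF items and slightly longer visits. No new visit is needed.
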